1.2 Secondary Objectives

- Estimate the complete response (CR) rate according to the Lugano Classification⁸, duration of response (DOR), overall survival (OS) and progression-free survival (PFS) in patients treated with pembrolizumab plus pralatrexate.
- Estimate the ORR and CR rate according to the International Harmonization Project response criteria (Cheson 2007).⁹
- Evaluate responses and disease progression according to the [Lymphoma Response to Immunomodulatory therapy Criteria \(LYRIC\)](#).¹⁰

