5.7 Replacement of Subjects

During the Phase 1 portion of the study, subjects will be replaced for any of the following:

- Missed any doses of pralatrexate during the DLT period (not due to DLT).
- Did not receive the doses of pembrolizumab during the DLT period (not due to DLT).

Subjects who are replaced for missed doses may continue to receive study treatment if there is clear clinical benefit, but will not be included in DLT analysis.

During the Phase 2 portion of the study, subjects who did not receive at least 1 dose of pembrolizumab and 1 dose of pralatrexate, or who did not have a tumor response assessment (except due to progression of disease prior to the first tumor response assessment) will be replaced. If a patient discontinues study treatment prior to the first response assessment due to progressive disease, the treating physician is encouraged to obtain imaging to confirm progression.

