11.2 Clinical Endpoint Definitions

Overall Response Rate (ORR): Defined as the proportion of patients that have a documented CR or PR at any time during study treatment.

Complete Response (CR) rate: Defined as the proportion of patients that have a documented CR at any time during study treatment.

Duration of Response (DOR): Defined as the time from the first achievement of PR or CR to time of PD. Patients who never achieve PR or CR are excluded. Patient who has not had disease progression/relapse at last follow-up is censored at the time of last follow-up.

Overall Survival (OS): Defined as time from initiation of study therapy to death from any cause. If a patient is alive at the last evaluation time period, survival time is censored at the time of last follow-up.

Progression-Free Survival (PFS): Defined as the time from initiation of study therapy to the first observation of disease relapse/progression or death from any cause, whichever occurs first. If the patient has not progressed relapsed or died, the patient is censored at the time of last follow-up.

Toxicity: Toxicity and adverse events will be recorded using the NCI CTCAE 5.0 scale. Observed toxicities will be summarized by type (organ affected or laboratory determination such as absolute neutrophil

count), severity (by NCI CTCAE v5.0 and nadir or maximum values for lab measures), date of onset, duration, reversibility, and attribution.

Unacceptable Toxicity: defined as one of the following AEs that is at least possibly related to study treatment:

- Any **≥ grade 3 immune-related AE (IrAE)** that does not resolve to grade ≤ 1 within 7 days with the exception of:
 - Grade 3 immune-related hepatitis if ALT or AST < 8 x ULN or total bilirubin < 5 x ULN.
 - Grade 3 asymptomatic endocrinopathy.
 - Inflammatory response attributed to local antitumor response.
 - Vitiligo or alopecia of any grade.
- Any non-hematologic **grade 4 AE** that does not resolve to grade ≤ 1 within 7 days with the exception of:
 - Grade 4 asymptomatic lipase or amylase without evidence of pancreatitis
 - Grade 4 asymptomatic laboratory abnormalities including, but not limited to, hypo- or hyperglycemia, hypo- or hypernatremia, hypo- or hyperkalemia, hypo- or hypermagnesemia, hypo- or hyperphosphatemia, or hyperuricemia that do improve within 48 hours to Grade ≤ 2 with supportive measures.
 - Inflammatory response attributed to local antitumor response.
- Any Grade 5 AE.

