12.3.3 Analysis of Anti-tumor Activity

This study will aim to obtain an estimate of the anti-tumor activity of the study combination. ORR will be calculated as the proportion of evaluable patients that have confirmed CR or PR, as defined according to the 2014 Lugano Classification, exact 95% confidence intervals will be calculated for these estimates. Response rates will also be evaluated based on number and type of prior therapy(ies). Duration of response, as well as progression-free survival and overall survival will be estimated using the product-limit method of Kaplan and Meier. As secondary endpoints, the ORR and CR rate will also be estimated according to the International Harmonization Project response criteria (Cheson 2007).⁹

Any patient treated at the RP2D, including those from the Phase 1 portion, will be included in efficacy analyses. Patients will be evaluable for efficacy assessment if they received at least one dose of pralatrexate and at least one dose of pembrolizumab and underwent at least one response assessment. As discussed in [Section 5.7](#), patients will be evaluable for efficacy if they discontinued study therapy prior to the first response assessment because of progression of disease rather than solely because of unacceptable toxicity, withdrawal of consent, or investigator's decision.

12.3.4 Safety Analysis and Stopping Rules for Excessive Toxicity or for Rapid Disease Progression

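### Section 12.3.3 names no analysis set for PFS and OS, and on its more natural reading a death without progression before the first scan would drop out of both curves

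*Combined protocol and SAP*

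**What the plan says.** Section 11.2 starts both clocks at the first dose and counts every death. OS is "Defined as time from initiation of study therapy to death from any cause". PFS is "Defined as the time from initiation of study therapy to the first observation of disease relapse/progression or death from any cause". Neither definition mentions a scan. The secondary objective in Section 1.2 is to estimate "overall survival (OS) and progression-free survival (PFS) in patients treated with pembrolizumab plus pralatrexate".

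Section 12.3.3 is where these endpoints are analysed. It calculates ORR among evaluable patients and says that "progression-free survival and overall survival will be estimated using the product-limit method of Kaplan and Meier", without naming a population for the survival curves. Its next paragraph sets the population in three steps:

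- "Any patient treated at the RP2D, including those from the Phase 1 portion, will be included in efficacy analyses".
- A patient is evaluable for efficacy after at least one dose of each drug, provided the patient "underwent at least one response assessment".
- A patient who stopped before the first assessment still counts if this was "because of progression of disease rather than solely because of unacceptable toxicity, withdrawal of consent" or the investigator's decision.

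Section 5.7 follows the same line for Phase 2: subjects "who did not have a tumor response assessment (except due to progression of disease prior to the first tumor response assessment) will be replaced". Section 11.1 and the study calendar place the first on-treatment scan in cycle 4, days 15 to 21.

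**The concern.** If the evaluability condition governs PFS and OS, entry to a curve that starts at first dose depends on something that happens about eleven weeks later. The patient must reach a response assessment or stop earlier for progression. A patient who dies of toxicity or infection before then, without progression, meets neither condition. That death is an event for both endpoints by definition, yet it would not be in the analysis. This is guarantee-time (immortal-time) bias. Leaving out such deaths can only raise the curves after the first scan.

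The problem is separate from the choice of ORR denominator. OS needs no scan, and Kaplan-Meier already handles a patient who has none by counting the death or censoring at last contact. Early deaths on treatment are among the events that survival curves for a new combination should show.

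**Working it through.** **The plan's own figures.** No figure is stated for PFS or OS. The 24-patient basis can be checked on ORR. The standard error is √(0.3 × 0.7/24) = 9.4% at an ORR of 30% or 70%, and √(0.5 × 0.5/24) = 10.2% at 50%, as Section 12.1.2 states.

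**Timing.** Three 21-day cycles take 63 days. Day 15 of cycle 4 is therefore 77 days after first dose (63 + 14), and the cycle ends at 84 days: week 11 to 12 if nothing is delayed.

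**One patient traced through the text.** Suppose a patient receives both drugs at the RP2D on Day 1 and dies of a treatment-related infection in week 6, with no progression and no assessment.

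- Section 11.2: an OS event and a PFS event at week 6.
- Section 12.3.3, opening population sentence: included.
- Section 12.3.3, the two sentences after it: not evaluable, because there was no assessment and the patient did not stop for progression.
- Section 5.7, if enrolled in Phase 2: replaced.

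**Size.** The rate of such deaths is not in the documents. Assume that k of them occur beside 24 evaluable patients. The omitted share is e = k/(24 + k). For any time t after the first scan,

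S_evaluable(t) = S_treated(t)/(1 − e) = S_treated(t) × (24 + k)/24.

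To put this on a scale, take the single-agent medians quoted in Section 2.1.1 (OS 14.5 months, PFS 3.5 months) as the true all-treated values on exponential curves. This is an illustration, not a forecast. The true 12-month OS is then 2^(−12/14.5) = 56.3%. The reported median solves S_treated(t) = 0.5(1 − e), so it equals the true median × [1 + log2((24 + k)/24)].

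| k | e | Inflation factor | 12-month OS as reported | Median OS (months) | Median PFS (months) |
|---|---|---|---|---|---|
| 0 | 0 | 1.000 | 56.3% | 14.5 | 3.5 |
| 1 | 4.0% | 1.042 | 58.7% | 15.4 | 3.7 |
| 2 | 7.7% | 1.083 | 61.0% | 16.2 | 3.9 |

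With e rounded to 8%, the 12-month figure is 56.3%/0.92 = 61.2%.

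**Upper bound.** On the same exponential OS curve, deaths from all causes total 11.4% by day 77 and 12.4% by day 84. A share of e = 12%, which would give 56.3%/0.88 = 64.0% at 12 months, requires nearly every early death to be without progression. It is a ceiling, not a plausible case. Even e = 8% requires about two-thirds of early deaths to be of that kind (8/12.4 = 65%; 8/11.4 = 70%).

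**The case against.** A reader might infer that the plan removes early toxic deaths from PFS and OS and that both curves are therefore overstated. The documents do not support that as a settled fact, for these reasons.

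- **The text points both ways.** The population paragraph opens by including any patient treated at the RP2D. The word evaluable is attached by name only to ORR, and the synopsis and Section 12.1.2 describe the same dose-and-assessment test as evaluability for response. Section 11.2 puts no scan condition on OS or PFS, and Section 5.11 follows vital status in all participants. An all-treated reading for survival is possible.
- **The bias is conditional.** It needs at least one RP2D patient to die before the first assessment without progression. Early progressors are kept. Patients who stop for toxicity and survive are due a scan 12 weeks after their last one (study calendar, footnote r) and can then qualify.
- **The size is modest.** One or two omitted deaths move 12-month OS by 2.4 to 4.7 percentage points. The binomial standard error at 56.3% with 24 patients is √(0.563 × 0.437/24), about 10 points. PFS and OS are descriptive and drive no decision. Section 12.3.4 monitors possibly related deaths in all treated patients, and a second one halts accrual for review.

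The second and third arguments stand as limits on the finding. The first shows that the restriction is a reading rather than an explicit rule, but it does not remove the problem. If the opening sentence governed every efficacy analysis, the two sentences after it would have nothing to do. If it governed only survival, the section would need a distinction that it does not draw, and those two sentences speak of efficacy, not response. Safety monitoring protects patients but does not restore a death to a curve. Imprecision does not excuse an avoidable error in a known direction.

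**Conclusion.** The point holds as an unclear analysis set whose more natural reading is biased. Section 12.3.3 does not say which patients enter the PFS and OS curves. If its evaluability condition is applied, a death without progression before about week 11-12 is an event under Section 11.2 that appears in neither curve, and the result departs from the treated population in the secondary objective.

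With no such death there is no overstatement from this source. With one or two beside 24 evaluable patients, survival after the first scan would be inflated by about 4% or 8% in relative terms. These counts are assumptions; the months and percentages also rest on an exponential curve with single-agent historical medians. The loss falls mainly on early deaths and withdrawals. An excluded withdrawal would otherwise be censored, and its effect has no fixed direction. The ORR analysis and the two-stage rule are not affected by this point.

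Left open, the choice between the two readings could be made after the data are seen, in an open-label single-arm trial. It should be settled in the text.

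**What to change.** State in Section 12.3.3 that PFS and OS are estimated from first dose in all RP2D patients, from either phase, who received any study treatment, whether or not a response assessment was done. Confine the response-assessment condition, and its exception for early progression, to the response endpoints. Both drugs start on Day 1, so defining the set by any study treatment should differ little, if at all, from patients treated with the combination. Section 5.7 can stay as it is for filling the response-evaluable sample, provided a replaced patient remains in the PFS and OS analyses.

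The cost is about one sentence. Vital status is already followed for all participants (Section 5.11), and survival status is on the study calendar, so no new data, patients or design change are needed. The downside is that PFS and OS may look slightly less favourable.

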2.0 BACKGROUND

2.1 Introduction/Rationale for Development

2.1.1 Disease Under Study: Peripheral T-cell Lymphoma

Peripheral T-cell lymphomas (PTCL) are an uncommon group of disorders, accounting for about 10% of all non-Hodgkin lymphomas (NHL). EBV-associated extranodal NK/T-cell lymphoma (NKTCL) is more common in parts of Asia and South America, while angioimmunoblastic T-cell lymphoma (AITL) and peripheral T-cell lymphoma, not otherwise specified (PTCL NOS) are more common in Western countries.¹² TCLs are generally associated with poor outcomes after standard therapy, with variation in prognosis according to disease subtype.¹² ALK-expressing anaplastic large cell lymphomas (ALCL) have a favorable prognosis with 5-year survival exceeding 80%, though some studies suggest outcomes in ALCL are dependent on age rather than ALK status.¹²⁻¹⁴ Anthracycline-based induction combination chemotherapy is standard upfront treatment for patients with PTCL; however, with the exception of ALK-positive ALCL, relapse rates are high.¹⁵⁻¹⁷ Autologous hematopoietic stem cell transplantation (ASCT) is widely used as consolidation for PTCL patients in first remission to reduce the risk of relapse. Single-arm prospective and retrospective studies of consolidative ASCT for TCLs in 1st remission report improvements in survival compared to historical controls, but progression-free survival (PFS) remains low, ranging from 44-58% at 3-5 years.^{2,18-21} Outcomes are poorer in patients who undergo ASCT with relapsed PTCL, with 3-5 year PFS ranging from 32-41%.^{1,2}

Current approved therapies available for relapsed or refractory TCLs include histone deacetylase inhibitors (romidepsin and belinostat), pralatrexate, and brentuximab vedotin (for ALCL). With the exception of brentuximab vedotin for ALCL, these agents are associated with low response rates and short median progression free survival.³⁻⁵

In the pivotal PROPEL trial, 115 heavily pre-treated PTCL patients (median 3 prior systemic therapies) received pralatrexate as a single agent. The overall response rate (ORR) in 109 evaluable patients was 29%, including 12 (11%) complete responses (CR) and 20 (18%) partial responses (PR), with a median remission duration of 10.1 months. Median PFS and OS were 3.5 and 14.5 months, respectively. The most common grade 3/4 adverse events were thrombocytopenia (32%), mucositis (22%), neutropenia (22%), and anemia (18%).⁵

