16.5 Participant Withdrawal

Participants may withdraw from the study at any time and for any reason without prejudice. The withdrawal must be documented per institutional policies. The COH DCC should be promptly notified of the change in participant status.

Participant withdrawal may consist of any of the following with regard to study procedures and data collection:

- Withdrawal from study treatment, but agreement to continue with active study procedures and chart review and survival follow-up.
- Withdrawal from study treatment and all active procedures, but agreement for chart review and survival follow-up.
- Withdrawal from study treatment, all active procedures, and any future data collection.

Participants who agreed to the collection of research blood samples may withdraw consent to use their specimens, if they are not yet processed as detailed in the consent form. Once the PI and site PI is notified of this withdrawal of informed consent, the research specimens will not be used in any research. At that time, any of the existing specimens will be destroyed.

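### The primary ORR leaves out RP2D patients never assessed for a reason other than progression, against the opening sentence of its own paragraph, and its numerator is worded differently in Sections 11.2 and 12.3.3

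*Combined protocol and SAP*

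**What the plan says.** **Denominator.** The efficacy paragraph of Section 12.3.3 opens by placing everyone treated at the RP2D, Phase 1 patients among them, in the efficacy analyses. It then restricts evaluability to patients who received "at least one dose of pralatrexate and at least one dose of pembrolizumab and underwent at least one response assessment". A second route admits patients who stopped "prior to the first response assessment because of progression of disease rather than solely because of unacceptable toxicity, withdrawal of consent" or investigator's decision. Section 5.7 applies the same rule to replacement in Phase 2: patients who did not receive both drugs, "or who did not have a tumor response assessment (except due to progression of disease prior to the first tumor response assessment) will be replaced". Section 12.1.2 sets the final number at 24 evaluable patients.

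**Numerator.** Section 11.2 defines ORR as follows: "Defined as the proportion of patients that have a documented CR or PR at any time during study treatment". Section 12.3.3 says "ORR will be calculated as the proportion of evaluable patients that have confirmed CR or PR", by the 2014 Lugano Classification. Section 11.1 describes confirmation for CR only: PET/CT where the disease is FDG-avid, and bone marrow. Neither Section 11.1 nor the Lugano table in Appendix B has a confirmation step for PR.

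**Timing.** The first on-treatment scan falls in cycle 4 (Section 11.1), between days 15 and 21 with a 3-day allowance (Section 10.0, footnote g). Under footnote r, patients who stop for a reason other than progression are scanned 12 weeks after their last scan.

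**The concern.** Whether a patient enters the denominator depends on what happens after treatment starts. Someone treated at the RP2D who stops for toxicity, withdraws, is taken off by the investigator, or dies without progression before any post-baseline scan is removed and replaced. None of these patients can have a documented response. The response-evaluable ORR is therefore at least as high as the ORR among all treated patients. The first scan is some 11 to 12 weeks in, and tolerability is itself a primary objective, so early loss for such reasons deserves to be visible in the efficacy estimate.

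The text does not settle the denominator. An analyst could defend all treated patients from the opening sentence of the paragraph, or evaluable patients from the sentences after it. The numerator has a similar gap: a PR seen on one scan counts under Section 11.2, and may or may not count under Section 12.3.3, depending on what confirmed is taken to mean. Both choices should be fixed before responses are known.

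**Working it through.** **1. The plan's own precision figures (Section 12.1.2).**
- SE = sqrt(p(1-p)/24): sqrt(0.3 × 0.7/24) = 9.4% at an ORR of 30% or 70%, and sqrt(0.5 × 0.5/24) = 10.2% at 50%. This agrees with the stated 9.4-10.2%.
- The widest exact (Clopper-Pearson) 95% interval with n = 24 is at 12/24, with width 41.8%. The plan rounds this to 42%.
- Stage 1: 1 - 0.65^7 = 0.951, which agrees with the stated chance of at least 95%.

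The design arithmetic is right for 24 evaluable patients. The point is who and what is counted.

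**2. Time at risk of never being assessed.** Cycle 4 day 15 is 3 × 21 + 15 = day 78, and day 21 is day 84. With the 3-day allowance, the first scan falls at about days 75-84.

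**3. Direction.** With x responders among 24 evaluable patients and m treated but never assessed, x/24 ≥ x/(24 + m), with equality only if x = 0 or m = 0.

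**4. Size for the denominator (m is assumed; the documents give no rate).** Take x = 8:
- m = 0: 8/24 = 33.3% (exact 95% CI 15.6-55.3)
- m = 1: 8/25 = 32.0%, a shift of 1.3 points
- m = 2: 8/26 = 30.8% (14.3-51.8), a shift of 2.6 points
- m = 3: 8/27 = 29.6% (13.8-50.2), a shift of 3.7 points

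Why one to three? In the single-agent benchmark (Section 2.1.1), "115 heavily pre-treated PTCL patients (median 3 prior systemic therapies) received pralatrexate as a single agent" and 109 were evaluable, so 6/115 = 5.2% were not. The reasons are not given, so this is only a rough guide and not a never-assessed rate. At 5.2%, reaching 24 evaluable patients takes 24 × 115/109 = 25.3 treated on average. The number left out is negative binomial with evaluable probability 109/115, and the chance of three or fewer is 0.950.

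The accrual cap does not rule out more. It leaves 40 - 36 = 4 to 40 - 30 = 10 places for inevaluable patients of every kind, including Phase 1 replacements for missed doses. Four never-assessed RP2D patients would give 8/28 = 28.6%. Ten, an extreme in which every spare place is used this way, would give 8/34 = 23.5%, a shift of about one standard error.

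**5. Size for the numerator.** One response counted under one definition and not the other moves the ORR by 1/24 = 4.2 points. The documents give no basis for how many there would be.

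**6. Comparability with the benchmark.** The 29% is (12 + 20)/109 = 29.4%. Over all who received drug it is 32/115 = 27.8%.

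**The case against.** The evaluable set is a pre-specified and disclosed choice, stated consistently in the synopsis and in Sections 5.7, 12.1.2 and 12.3.3, and it matches the basis of the 29% benchmark. The most damaging exclusion is prevented, because early progressors stay in. The trial is a single-arm estimation study with no final test and no ORR threshold, so no decision turns on a few points. All of this stands, and it is why the point is a modest one. It does not reconcile the paragraph's opening sentence with its later sentences, or the two numerators.

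Some stronger readings are tempting, but the documents do not support them:
- *Every early toxicity stop is excluded.* Footnote r schedules a scan for such patients, and one who has it has been assessed. Similarly, Section 16.5 allows "Withdrawal from study treatment and all active procedures, but agreement for chart review and survival follow-up", so a standard-of-care scan might still be captured after withdrawal. Only patients with no post-baseline assessment at all are lost.
- *The numerator mismatch costs several points.* No rule in the documents could make a PR fail confirmation, and confirmed can be read as simply established under Lugano and Section 11.1. Any assumed number of unconfirmed PRs has no source.
- *A lower non-evaluable rate follows from the n = 111 in Section 2.3.* That analysis reports 27% of 111, about 30 responders, against 32 in Section 2.1.1. The two analyses disagree and cannot be subtracted from each other.
- *Responses after Lugano progression should be barred.* Section 5.10 allows treatment to continue through an indeterminate response, and Section 11.2 counts a response at any time on treatment. A bar would be a new restriction, not a correction.

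**Conclusion.** The concern holds as a low-cost improvement. Sections 12.3.3 and 5.7 together leave out and replace RP2D patients who were never assessed for a reason other than progression. The effect on the ORR is upward or nil, and the rule contradicts the opening sentence of its own paragraph. The documented/confirmed mismatch is a real ambiguity in the primary numerator, since nothing says how a PR is confirmed.

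The likely size is small: 1.3 to 3.7 points if one to three patients are left out and eight respond, well inside the stated standard error. Both counts are assumptions. A reader might infer that the reported ORR would be materially inflated, but the documents give no rate that would show this. The direction is certain; the amount is not.

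**What to change.** In Section 12.3.3, give effect to the opening sentence. Calculate the ORR with its exact 95% CI over all patients treated at the RP2D, and count as a non-responder anyone with no post-baseline assessment for any reason, including patients who were replaced. All treated should also take in a patient who received only one of the two drugs. Such a patient can arise because pembrolizumab is given first (Section 5.8.1), and the present rule leaves that patient out.

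Report the response-evaluable ORR alongside, because the 29% benchmark (109 evaluable of 115) is on that basis.

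Use documented CR or PR per Lugano in both Section 11.2 and Section 12.3.3, and keep the PET/CT and marrow confirmation of CR in Section 11.1.

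Leave the 0/7 stage-1 rule, replacement to 24 evaluable patients and the accrual cap of 40 as they are.

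The cost is wording in two sections and one extra analysis, with no new data. The downsides are a slightly lower reported ORR and a primary estimate on a different basis from the benchmark, which the second estimate covers.
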